10.4.1.1.1. Suspected Unexpected Serious Adverse Reactions

Suspected unexpected serious adverse reactions (SUSARs) are serious events that are not listed in the IB and that the investigator identifies as related to study drug or procedure. United States 21 CFR 312.32 and European Union Clinical Trial Directive 2001/20/EC and the associated detailed guidances or national regulatory requirements in participating countries require the reporting of SUSARs. Lilly has procedures that will be followed for the recording and expedited reporting of SUSARs that are consistent with global regulations and the associated detailed guidances.

10.4.1.2. Adverse Events of Interest

10.4.1.2.1. Hypoglycemia

Patients and their parents or legal guardians will be trained about signs and symptoms of hypoglycemia, how to treat hypoglycemia, and how to collect appropriate information in the study diary according to the Study Schedule ([Attachment 1](#)).

Hypoglycemia will be classified as follows (the plasma glucose [PG] values in this section refer to values determined by a laboratory or International Federation of Clinical Chemistry and Laboratory Medicine plasma-equivalent glucose meters and strips) (ADA 2005, 2020):

- Documented symptomatic hypoglycemia is defined as any time a patient feels that he/she is experiencing symptoms and/or signs associated with hypoglycemia, and has a PG level of <70 mg/dL (<3.9 mmol/L).
- Asymptomatic hypoglycemia is defined as an event not accompanied by typical symptoms of hypoglycemia but with a measured PG of <70 mg/dL (<3.9 mmol/L).
- Probable symptomatic hypoglycemia is defined as an event during which symptoms of hypoglycemia are not accompanied by a PG determination (but that was presumably caused by a PG concentration of <70 mg/dL [<3.9 mmol/L]).
- Severe hypoglycemia is defined as an episode requiring the assistance of another person to actively administer carbohydrate, glucagon, or other resuscitative actions. These episodes may be associated with sufficient neuroglycopenia to induce seizure or coma. Plasma glucose measurements may not be available during such an event, but neurological recovery attributable to the restoration of PG to normal is considered sufficient evidence that the event was induced by a low PG concentration.
- Nocturnal hypoglycemia is defined as any hypoglycemic event that occurs between bedtime and waking.

Cases of relative hypoglycemia, defined as symptomatic events during which the person reports any of the typical symptoms of hypoglycemia and interprets those as indicative of hypoglycemia, but with a measured PG concentration of ≥ 70 mg/dL (≥ 3.9 mmol/L), will also be collected.

Certain categories of hypoglycemia will also be evaluated using a PG cutoff < 54 mg/dL (< 3.0 mmol/L) (International Hypoglycaemia Study Group 2017).

If a hypoglycemic event meets the criteria of severe, it needs to be recorded as serious on the AE CRF and reported to Lilly as an SAE.

10.4.1.2.2. Pancreatitis

Acute pancreatitis is an acute inflammatory process of the pancreas that may also involve peripancreatic tissues and/or remote organ systems (Banks and Freeman 2006). The diagnosis of acute pancreatitis requires 2 of the following 3 features:

1. Abdominal pain, characteristic of acute pancreatitis (generally located in the epigastrium and radiating to the back in approximately half the cases [Banks and Freeman 2006; Koizumi et al. 2006]; the pain is often associated with nausea and vomiting)
2. Serum amylase (total and/or pancreatic) and/or lipase $\geq 3 \times \text{ULN}$
3. Characteristic findings of acute pancreatitis on imaging, such as contrast-enhanced computed tomography (CT) scan, or less commonly, magnetic resonance imaging (MRI), or transabdominal ultrasound.

If acute pancreatitis is suspected, appropriate laboratory tests (including levels of amylase [total and pancreatic] and lipase) should be obtained via the central laboratory (and locally, if needed). Imaging studies, such as abdominal CT scan with (or without) contrast, MRI, or ultrasound (transabdominal or endoscopic), should be performed as appropriate. If evaluation supports the diagnosis of acute pancreatitis, the patient must permanently discontinue therapy with study drug. The most appropriate diabetes therapeutic regimen will be decided on by the investigator, based on the patient's clinical status. A review of the patient's concomitant medications should be conducted to assess any potential causal relationship with pancreatitis.

Each AE of pancreatitis must be reported. If typical signs and/or symptoms of pancreatitis are present and confirmed by laboratory values (lipase or amylase) and imaging studies, the event must be reported as an SAE. For a potential case that does not meet all of these criteria, it is up to the investigator to determine the seriousness of the case (AE or SAE) and the relatedness of the event to study drug.

In addition to the diagnostic assessment in patients who develop symptoms of acute pancreatitis, each patient will have measurements of amylase (total and pancreatic) and lipase during the trial to assess any potential effects of dulaglutide on the exocrine pancreas (refer to the Study Schedule, [Attachment 1](#)). Further diagnostic assessment per the Lilly algorithm for the assessment of asymptomatic elevated pancreatic enzymes will be required whenever lipase and/or amylase (pancreatic and/or total) are $\geq 3 \times \text{ULN}$ at any time during the study.

All AEs of acute or chronic pancreatitis, as well as cases of lipase or amylase values that are confirmed $\geq 3 \times \text{ULN}$, will be adjudicated by a group of physicians external to Lilly. In addition,

AEs of severe or serious abdominal pain of unknown origin will also be submitted for adjudication to assess for possible pancreatitis or other pancreatic disease. Relevant data from patients with acute pancreatitis, those with severe or serious abdominal pain of unknown origin, and those that undergo additional assessments due to confirmed elevated pancreatic enzymes will be entered into a specifically designed electronic CRF or eCRF page by study site or Lilly staff. The adjudicators will enter the results of adjudication in a corresponding eCRF page.

10.4.1.2.3. Thyroid C-Cell Hyperplasia and C-Cell Neoplasms

Individuals with a known personal or family history of MEN 2A or 2B, thyroid C-cell hyperplasia, medullary thyroid carcinoma, or a serum calcitonin ≥ 20 pg/mL at screening will be excluded from the study (see Section 8.2). The assessment of thyroid safety during the trial will include reporting of thyroid TEAEs and measurements of serum calcitonin according to the Study Schedule ([Attachment 1](#)) at screening, baseline, and periodically throughout the study. The purpose of serum calcitonin measurements is to assess the potential of dulaglutide versus other background medications to affect thyroid C-cell function, which may indicate development of C-cell hyperplasia and neoplasms.

Patients who develop serum calcitonin increases $\geq 50\%$ of the baseline value AND an absolute value ≥ 20 pg/mL and < 35 pg/mL at Visit 9 (Week 26) or Visit 16 (Week 52) will be asked to repeat the measurement within 1 month. If this repeat value is increasing ($\geq 10\%$ increase), the patient will be recommended to undergo additional endocrine assessment and longer term follow-up by an endocrinologist to exclude a serious adverse effect on the gland. Patients with an increase in serum calcitonin $\geq 50\%$ of the baseline value AND an absolute value ≥ 35 pg/mL at Visit 9 (Week 26) or Visit 16 (Week 52) will be recommended to immediately undergo additional endocrine assessments and longer term follow-up by an endocrinologist.

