Additional secondary efficacy endpoints are the following:

- Change in FBG between baseline and Week 26 and Week 52
- Percentage of patients achieving a target HbA1c <7.0% at Week 26 and Week 52
- Change in BMI from baseline to Week 26 and Week 52
- Change in HbA1c measured in the central laboratory from baseline to Week 26 and Week 52

Safety: Secondary safety endpoints include:

- Incidence of hypoglycemic episodes and the need for rescue due to hyperglycemia at Weeks 26 and 52
- Incidence of pancreatitis and change from baseline in pancreatic enzymes to Weeks 26 and 52
- Incidence of thyroid TEAEs and change from baseline in serum calcitonin to Weeks 26 and 52
- Incidence of dulaglutide ADAs and the incidence of allergic, hypersensitivity, and injection site reactions at Weeks 26 and 52

Pharmacokinetics: Venous blood samples to measure the plasma concentrations of dulaglutide using validated bioanalytical assays.

Pharmacodynamics: Endpoints may include, but are not necessarily limited to, endpoints for efficacy (HbA1c, glucose) and safety (blood pressure, heart rate). The relationship between dulaglutide dose and/or concentration and safety and efficacy measures and patient or study factors that may influence PK or PD responses will be performed using all available patient data.

Health Outcomes: To compare the effect of dulaglutide compared to placebo on health status, as measured by the change from baseline to Week 26 and to assess the following at Week 52 in the validated patient-reported outcome (PRO) measure, EQ-5D-Y.

Statistical Methods:**Determination of Sample Size:**

A sample size of approximately 150 will be enrolled (50 patients per arm), in order to obtain 120 completers at 26 weeks. This sample size provides at least 90% power for demonstrating superiority of the pooled dulaglutide 0.75 mg and 1.5 mg arms compared to placebo (primary objective), with a mean difference in change from baseline in HbA1c of -0.65% and standard deviation of 1%, assuming a dropout rate of 20%. Under the same assumptions, each individual dulaglutide arm will have at least 80% power to demonstrate superiority over placebo. The screen failure rate is estimated as 80%. Among the completers, there will be no more than 25% of patients who, at baseline, were treated with diet and exercise only and who are metformin naïve.

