- If a female is of childbearing potential, the use of effective contraception will be discussed (see [Attachment 4](#)).
- Study diaries will be collected and the following reviewed:
 - Self-monitoring of blood glucose results
 - Hypoglycemia events
 - Adverse event information
 - The date and time of all study drug injections
 - Females: The date of the last menstrual period
- A local urine pregnancy test will be performed for all females of childbearing potential.
- The patient will receive:
 - Study diaries
 - Glucometer supplies
 - Diet and exercise instruction for their T2DM
 - Study drug. (At this visit, those patients who were assigned in a blinded fashion to 1.5 mg dulaglutide will be titrated from 0.75 mg/week to 1.5 mg/week. Therefore, prior to dispensing study drug to any patient, the physician will confirm via IWRS that the patient tolerated the previous 4 weeks of blinded study drug.)

The patient will be sent home with appointments for 1 telephone visit, which will occur in 5 weeks (Week 9) and for a clinic visit in 9 weeks (Week 13) in the fasted state.

Week 9: Telephone Visit (Visit Window up to ± 7 days)

At this visit, the following will be performed:

- Concomitant medication information will be documented
- If a female is of childbearing potential, the use of effective contraception will be discussed (see [Attachment 4](#)).
- The contents of the study diaries for the previous month will be reviewed:
 - Self-monitoring of blood glucose results
 - Hypoglycemia events
 - Adverse event information
 - The date and time of all study drug injections
 - Females: The date of the last menstrual period

Week 13: Clinic Visit (Visit Window up to ± 7 days)

At the half-way point in the double-blind portion of the clinical trial, the patient will return to the clinic in the fasted state. This visit must occur on the date of the patient's usual weekly injection of study drug, and before injection of study drug, as the patient will undergo collection of blood for a pre dose PK level at this visit, inject study drug and have a post dose PK level drawn. The following will be performed:

- Blood will be collected for a predose PK level, noting the exact date and time.*
- This will be followed by injection of study drug, noting the exact date and time.
- A symptom-directed physical exam by a physician will be performed.
- Vital signs will be measured, along with height, weight, and waist circumference.

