- Concomitant medication information will be documented.
- If a female is of childbearing potential, the use of effective contraception will be discussed (see [Attachment 4](#)).
- Study diaries will be collected and the following reviewed:
 - Self-monitoring of blood glucose results
 - Hypoglycemia events
 - Adverse event information
 - The date and time of all study drug injections
 - Females: The date of the last menstrual period
- The patient will receive:
 - Study diaries
 - Glucometer supplies
 - Diet and exercise instruction for their T2DM
 - Study drug
- The visit will conclude with another collection of blood for PK (this post dose PK level must be drawn at least 1 hour and up to 12 hours after study drug injection) noting the exact date and time and the elapsed time since study drug injection.*

The patient will be sent home with appointments for 2 telephone visits, which will occur in 5 and 9 weeks (Weeks 18 and 22), and a clinic visit in 13 weeks (Week 26) in the fasted state for the final double-blind visit.

*All other laboratories required to be collected at this visit (including ADAs) may be collected with either the first or the second blood draw. In females of childbearing potential, the laboratories will include a serum pregnancy test (a local urine pregnancy test must also be performed).

Weeks 18 and 22: Telephone Visits (Visit Window up to ± 7 days)

At these visits, the following will be performed:

- Concomitant medication will be documented.
- If a female is of childbearing potential, the use of effective contraception will be discussed (see [Attachment 4](#)).
- The contents of the study diaries for the previous month will be reviewed:
 - Self-monitoring of blood glucose results
 - Hypoglycemia events
 - Adverse event information
 - The date and time of all study drug injections
 - Females: The date of the last menstrual period

Week 26: Final Double-Blind Visit (Visit Window up to ± 6 days)

At the final visit for the double-blind portion of the trial, patients will return to the clinic in the morning in the fasted state. This visit must occur on the date of the patient's usual weekly injection of study drug and before the patient has injected study drug, as blood will be collected for a pre-dose PK level prior to study drug injection.

The following will be performed:

- A physician will perform a physical exam and Tanner staging.
- Vital signs will be measured, along with height, weight, and waist circumference.

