	Screen	Random- ization	Phone visit	Clinic visit	Phone visit	Clinic visit	Phone visit	Phone visit	Clinic visit	Phone visit	Phone visit	Phone visit	Clinic visit	Phone visit	Phone visit	Clinic visit	Clinic visit	Clinic visit			
Visit	V1	V2	V3	V4	V5	V6	V7	V8	V9	V10	V11	V12	V13	V14	V15	ET	V16	V801			
Week	-4	0	1	4	9	13	18	22	26	27	31	35	39	44	48		52	56			
Allowed Visit Intervals (D)	±7	0	±3	±7	±7	±7	±7	±7	±6	+7	±7	±7	±7	±7	±7	±7	±7	±7			
Fasting visit			X				X											X			
Islet cell Ab (IA2)	X																				
Anti-GAD Ab (GAD65)	X																				
Standard clinical chemistries and hematology ^l	X	X				X			X								X	X			
Random blood glucose	X																X		X		
Fasting blood glucose		X				X			X										X		
HbA1c	X	X				X			X									X	X	X	
Amylase, (P) amylase, lipase	X	X				X			X									X	X	X	
Serum calcitonin	X	X				X			X									X	X	X	
Serum hormones ^m		X							X										X	X	
Urinalysis		X							X										X	X	
Spot urine ACR		X							X										X	X	
Serum pregnancy test ^d	X					X			X									X		X	X
Urine pregnancy test	X ⁿ	X	X ⁿ	X	X ⁿ	X	X ⁿ	X ⁿ	X	X ⁿ	X ⁿ	X ⁿ	X	X ⁿ	X ⁿ	X	X ⁿ	X	X		
Fasting insulin		X				X			X												
Fasting C-peptide		X				X			X												
Fasting adiponectin		X				X			X												
LY2189265 plasma concentrations ^o						X, X			X									X	X	X	
Anti-LY antibodies ^p		X				X			X									X	X	X	
EQ-5D-Youth instrument		X							X									X	X		

Study Schedule, Protocol H9X-MC-GBGC

Abbreviations: Ab = antibodies; ACR = albumin/creatinine ratio; ADA = anti-drug antibodies; AE = adverse event; BMI = body mass index; D = days; ECG = 12-lead electrocardiogram; ET = early termination; GAD65 = glutamic acid decarboxylase 65 autoantibodies; HbA1c = hemoglobin A1c; HO = health outcomes; IA2 = tyrosine phosphatase-like insulinoma antigen 2 autoantibodies; IGF-1 = insulin-like growth factor -1; IWRS = Interactive Web-Response System; LH = luteinizing hormone; LY = dulaglutide; PK = pharmacokinetics; QOL = quality of life; SMBG = self-monitored blood glucose; V = visit; V801 = safety follow-up visit; W = week.

- a At Visit 4, the physician will determine whether the patient tolerated the first 4 weeks of study drug. If the patient tolerated the study drug, they will be given their assigned study drug.
- b Height, weight, and waist circumference are measured per [Attachment 6](#).

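### Both calcitonin action tiers name only Weeks 26 and 52, so a qualifying rise at the scheduled Week 13 draw has no protocol-specified repeat or referral

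*Protocol*

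**What the plan says.** Protocol Section 10.4.1.2.3 defines two action tiers, both requiring a rise of at least 50% over baseline.

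- Lower tier, 20 to <35 pg/mL: patients with such a value "at Visit 9 (Week 26) or Visit 16 (Week 52) will be asked to repeat the measurement within 1 month". If the repeat is at least 10% higher, endocrine assessment and longer follow-up are recommended.
- Upper tier, 35 pg/mL or more: patients with such a value "at Visit 9 (Week 26) or Visit 16 (Week 52) will be recommended to immediately undergo additional endocrine assessments".

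The section gives the purpose of the test as "to assess the potential of dulaglutide versus other background medications to affect thyroid C-cell function", because a change could point to C-cell hyperplasia or neoplasm. It says sampling follows the Study Schedule.

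In Attachment 1, the row "Serum calcitonin" is marked at Visits 1, 2, 6 (Week 13) and 9 (Week 26), with further marks later. The synopsis lists the secondary safety endpoint as "change from baseline in serum calcitonin to Weeks 26 and 52".

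Under Protocol Section 10.5.1, calcitonin is not among the hormones withheld from sites.

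**The concern.** The sample is taken at Week 13 and the result goes back to the site, but the response is written for two other visits. A child with 40 pg/mL and a rise of at least 50% at Week 26 is recommended for immediate endocrine assessment. The same value at Week 13 prompts nothing in the protocol. Yet a value of 20 pg/mL or more at screening would have kept that child out of the trial (exclusion criterion 13).

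The protocol's other laboratory safety rules are not tied to visits in this way. The pancreatic enzyme work-up in Section 10.4.1.2.2 applies at any time during the study, and hepatic monitoring in Section 10.4.3 starts whenever the abnormality is seen. The documents give no reason for treating calcitonin differently.

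What is at stake is consistent follow-up of the individual child, not the treatment comparison.

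**Working it through.** **1. Is there a Week 13 draw?** Lined up against the visit header, the first four marks in the calcitonin row of Attachment 1 fall on Visits 1, 2, 6 and 9. The fasting insulin row shows the same marks at Visits 2, 6 and 9, and Protocol Section 10.1.3 places the insulin measures at Weeks 0, 13 and 26, so the columns up to Visit 9 can be relied on. After Visit 9 the extracted row runs past the end of the header, and no conclusion is drawn from it.

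**2. Does any other text supply an action?**

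- Protocol Section 8.3.2 stops study drug for exclusion criteria 11 and 12, among others, but not for criterion 13 (calcitonin).
- Protocol Section 10.5.1 requires documented review of laboratory reports but prescribes no response.
- Protocol Section 7.1 allows optional visits if medically necessary.
- Protocol Section 10.4.3 provides periodic blinded sponsor review. Protocol Section 12.2.11.1 provides DMC review about every 6 months, and SAP Section 6.1.1 allows annual review if enrollment is slow.
- SAP Sections 5.15.2.3 and 5.15.8 only list and summarize calcitonin.

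None of these is a repeat or referral rule for a raised Week 13 value.

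**3. How long until the rule can apply?** The inputs, from Protocol Section 7.1, are "Week 13: Clinic Visit (Visit Window up to ± 7 days") and "Week 26: Final Double-Blind Visit (Visit Window up to ± 6 days").

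- Nominal: 26 × 7 − 13 × 7 = 182 − 91 = 91 days = 13 weeks, which matches the interval the protocol states.
- Full windows: Week 13 falls on days 84 to 98 and Week 26 on days 176 to 188. Shortest 176 − 98 = 78 days (11.1 weeks); longest 188 − 84 = 104 days (14.9 weeks).
- Dosing-day limit: both visits must fall on the usual injection day, which is set at randomization. If that day is unchanged, the ±6-day window leaves only day 182 for Week 26, and Week 13 can be day 84, 91 or 98. The gap is then 98, 91 or 84 days. Reaching 78 or 104 needs a changed dosing day, which Section 9.5 permits.

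On either range the wait is more than twice the 1-month interval the protocol itself sets for a repeat.

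**4. What contact comes sooner?** At Week 13 the patient is given appointments for "2 telephone visits, which will occur in 5 and 9 weeks (Weeks 18 and 22"). Week 18 is nominally (18 − 13) × 7 = 35 days later. With its ±7-day window it falls on days 119 to 133, so the gap from Week 13 is 119 − 98 = 21 to 133 − 84 = 49 days. Section 7.1 allows any telephone visit to become face-to-face when medically necessary, so a repeat could sometimes be drawn then, within a month.

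**5. What if the rise does not last?** The Week 26 rule looks at the Week 26 value. A Week 13 rise that has dropped below threshold by then never meets either tier.

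**The case against.** The best defense is that Weeks 26 and 52 are the endpoint visits for calcitonin, so tying the formal triggers to them is a deliberate and defensible choice. Practical protection also exists: sites see every calcitonin result and must document laboratory review, the investigator is responsible for the child's care, optional visits are allowed, and patients with raised screening calcitonin or a relevant thyroid or MEN 2 history are excluded. A rise that persists meets the rule at Week 26 anyway.

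Most of this stands, and it bounds the consequence. It does not supply the missing rule. An endpoint visit defines a group comparison; it is not a reason to limit individual follow-up to that visit when the earlier sample is already in hand. Section 10.4.1.2.3 itself does not leave Week 26 to discretion, and a site that sees two visits named may conclude that nothing is expected at others.

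A reader might infer that every affected child waits up to 104 days. That needs a changed dosing day; otherwise the limit is 98. A reader might also infer that a Week 13 repeat always needs a separate extra visit. It does not, given the Week 18 window and the option to convert that contact. Nor do the documents support a claim about whether Week 39, early termination or Visit 801 carries a calcitonin draw outside the rule: the schedule as extracted is unclear after Visit 9, and the point does not depend on it.

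**Conclusion.** The gap is real but limited. A Week 13 calcitonin value of at least 20 pg/mL with a rise of at least 50% has no protocol-specified repeat or referral. The rule can first apply nominally 91 days later (84 to 98 days with an unchanged dosing day, 78 to 104 at the outer windows), and not at all if the value has fallen back. Until then, action depends on the investigator.

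This rests on reading the Visit 6 mark in Attachment 1 as a calcitonin draw, which the column alignment supports but no prose states separately.

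A reader might infer that children are harmed by the wait, or that the arms are compared unfairly. The documents support neither. They give no rate of calcitonin rises, so the number affected cannot be estimated; they do not show that earlier action changes outcome; and the wording applies equally to all arms. Efficacy, power and type I error are unaffected. It is a cheap patient-safety improvement that the sponsor should make.

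**What to change.** In both tiers of Protocol Section 10.4.1.2.3, replace the phrase naming Visits 9 and 16 with 'at any scheduled post-baseline calcitonin measurement'. Add one sentence: 'The 1-month repeat is assessed only against the 10% increase rule or the 35 pg/mL tier, and does not itself trigger a further repeat.' Without it, a stable value could keep triggering repeats: at 25 pg/mL, a 10% increase means 25 × 1.10 = 27.5 pg/mL, so an unchanged repeat of 25 would meet no referral criterion yet still sit in the lower tier.

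Thresholds and actions stay as they are, and no scheduled visit is added. The cost is an occasional extra repeat draw, taken at an optional visit or at the Week 18 contact converted to face-to-face if it falls within 1 month, and possibly a few extra endocrine referrals.
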